6.9 Continuation of Therapy

All participants in the intervention group will be free to continue with the therapy if they are happy with the product and procedure. Participants in the control group will be free to pursue TAI with their treating clinicians but this will not be supported or supervised by the trial.

7 STUDY VISITS AND PROCEDURES SCHEDULE

Procedure Schedule	Screening and recruitment	Assessment at baseline		Intervention	Assessment at 6- weeks post randomisation	
	-6 to -1 week	-7 to 0 days		Week 1 - 6	Week 7	
Protocol Activity:		1st visit	2nd visit		1st visit	2nd visit
Informed Consent	✓					
Eligibility Checklist	✓					
Demographic details	✓					
Procure TAI Device	✓					
Training on how to use TAI	✓					
Randomisation			✓			
Adverse Events Check		✓	✓	✓✓✓✓✓✓	✓	✓
Outcome measures:						
Neurogenic Bowel Dysfunction Score		✓	✓		✓	✓
Time to complete bowel care (assessor)		✓	✓		✓	✓
Time to complete bowel care (participant)		✓	✓	✓✓		
CCCSS		✓	✓		✓	✓
St Mark's Scale		✓	✓		✓	✓
SCI-QOL, BMD		✓	✓		✓	✓
Global Impression of Change					✓	✓
Blinding question Assessor		✓	✓		✓	✓
End of Study checklist						✓

8 CLINICAL AND LABORATORY ASSESSMENTS

This trial does not involve collection of human tissue, blood or body fluids.

There will be a mix of demographic data and outcome measure assessments collected by the same blinded assessor during the face to face assessments at baseline and 6 weeks post randomisation as per study visit and procedures schedule.

9 ADVERSE EVENT REPORTING

9.1 Definitions

9.1.1 Adverse Event (AE)

An adverse event (AE) for medicines, also referred to as an adverse experience, is any untoward medical occurrence in a participant administered a pharmaceutical product which does not necessarily have a causal relationship with this treatment.

An adverse event can therefore be any unfavourable and unintended sign, symptom, or disease temporally associated with the use of a medicinal (investigational) product, whether or not related to the medicinal (investigational) product (37).

9.1.2 Adverse Reaction (AR)

An Adverse Reaction (AR) is any untoward and unintended response to an investigational medicinal product related to any dose administered to a participant. All adverse events determined to have a reasonable possibility to have been caused by the medicinal product are considered to be adverse reactions (37).

9.1.3 Adverse Device Effect (ADE)

An Adverse Device Effect (ADE) is any adverse event related to the use of an investigational medical device. It includes events resulting from insufficient or inadequate Instructions for use, or any malfunction of the investigational medical device. It also covers any event resulting from use error or from intentional misuse of the investigational medical device (37).

9.1.4 Device Adverse Event (DAE)

A Device Adverse Event (DAE) is any untoward medical occurrence, unintended disease or injury, or untoward clinical signs (including abnormal laboratory findings) in participants, users or other persons, whether or not related to the investigational medical device. It includes events related to the procedures involved in using the device. A DAE for users or other persons is restricted to events related to the investigational medical devices (37).

9.1.5 Expected Occurrence (EO)

An Expected Occurrence (EO) is an adverse event or reaction that is highly prevalent in people with chronic SCD and very unlikely to be related to the clinical trial intervention. This includes urinary incontinence, urinary tract infection, respiratory infection, constipation, faecal incontinence, haemorrhoids, autonomic dysreflexia, pressure injury, hypotension, and spasticity. These will only be reported as adverse events if the investigator considers their occurrence to be a result of participation in the clinical trial.

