2. INTRODUCTION AND BACKGROUND

2.1 Background Information

Spinal Cord Injury (SCI) and Spina Bifida (SB) are two common causes of Spinal Cord Disorders (SCD). Both conditions can cause neurogenic bowel dysfunction (NBD) (4, 5). The severity of NBD is linked to the level of injury and 'completeness' of the lesion (6). Primary symptoms of NBD include constipation, incomplete bowel emptying and faecal incontinence (5).

A major goal of bowel care for individuals with SCD is timely and effective defaecation. This relies upon management of multiple factors. In New South Wales (NSW) and Queensland (QLD), most people with SCD are placed on a 'standard bowel care' program (7) which consists of:

- dietary management plus additional aperients to titrate stool consistency
- rectal medications (i.e. enema/suppositories) where appropriate
- digital stimulation or digital evacuation of stool
- stimulate the gastro-colonic reflex by eating breakfast before bowel care (8), and
- perform toileting at around the same time each day / second day.

Irrespective of these measures, bowel care can take a considerable amount of time and there are numerous reports in the literature to suggest that the length of time spent on bowel care can increase with time since injury (9). For example, people with NBD can spend over 90 minutes every day emptying their bowels. In addition, prolonged toileting can lead to complications such as haemorrhoids, anal fissures, dilation of the sigmoid colon, autonomic dysreflexia and pressure injuries. All can have a significant impact on physical and psychosocial wellbeing (10-14) as well as the ability to engage in vocational, recreational and social activities (15, 16). People with SCD rate bowel care as one of the most disabling aspects of SCD and of more importance to them than the inability to walk (4, 17). A particular aspect that people with SCD find most challenging is the time it takes to complete their bowel care routine (15, 18, 19) therefore it is a very disabling sequelae of SCD that requires attention.

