6.2 Eligibility Criteria

6.2.1 Inclusion Criteria

People will be eligible for inclusion if they:

- sustained a spinal cord injury more than 6 months prior or have Spina Bifida
- have a Neurogenic Bowel Dysfunction Score (3) ≥ 3
- are aged 18 years or over at the time of consent
- are willing to participate in the trial
- have been recommended to trial transanal irrigation by a clinician because they spend more than 30 mins on toileting AND ANY OF THE FOLLOWING:
 - had more than 1 episode of faecal incontinence per month
 - had a Bristol stool chart result of <3 or >6 for more than 3 cycles of bowel care
 - experienced abdominal symptoms such as bloating/cramping
 - experienced inconsistency with defaecation
 - experienced rectal symptoms (bleeding haemorrhoids, rectal prolapse, fissures etc)
 - experienced autonomic dysreflexia in response to bowel care

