6.8 Trial Closure

The trial will not be stopped for futility but will be stopped if there are reasons for concern about safety. All Adverse and Serious Adverse Events will be reviewed by a safety monitoring board with an independent medical monitor, [name] who will be consulted if there are any reasons for concern. There will be no follow-up of participants after their 6-week assessment.

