9.2 Assessment and Documentation of Adverse Events

All AEs will be evaluated by seriousness, causality and expectedness (38). All EOs will be identified on the Adverse Event/Reaction case report form (CRF) to differentiate between known, unexpected AE/ARs and ADE/DAEs. The Principal Coordinator along with Site Coordinators will conduct safety monitoring and reporting requirements for this study in accordance with the attached NSW Health policy directive i.e. only report SSI's to the HREC. Adverse event reporting will be included on the annual report to the NSLHD HREC.

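### Section 9.1.5 makes adverse-event reporting of bowel-care-related events depend on investigator attribution, against the protocol's own definitions and rationale, so those counts cannot be compared between arms

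*Protocol*

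**What the plan says.** Section 9.1.5 defines an EO as an event that is "highly prevalent in people with chronic SCD and very unlikely to be related to the clinical trial intervention". The list reads: "This includes urinary incontinence, urinary tract infection, respiratory infection, constipation, faecal incontinence, haemorrhoids, autonomic dysreflexia, pressure injury, hypotension, and spasticity". The reporting rule follows: "These will only be reported as adverse events if the investigator considers their occurrence to be a result of participation in the clinical trial".

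Section 9.2 then states "All EOs will be identified on the Adverse Event/Reaction case report form (CRF"), in order to tell event types apart. Section 10.2 says the same of the serious adverse event form.

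On oversight, section 6.8 says "All Adverse and Serious Adverse Events will be reviewed by a safety monitoring board" and gives concern about safety as the ground for stopping the trial. It does not mention EOs.

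**The concern.** The trial compares one way of carrying out bowel care with another, and several EO-listed events are ones that the protocol itself connects with bowel care. A category built on the presumption that they are unrelated, with a case-by-case attribution test before they are reported, takes them out of the ordinary adverse-event comparison.

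At stake is whether the trial can say anything reliable about these events, in either direction. An excess under transanal irrigation (TAI) could be under-reported, and so could a benefit. The safety board would be working from counts that had already passed through a causality judgement.

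**Working it through.** The protocol gives no rate for any EO, so there is no figure to reproduce. The check is mainly a comparison of sections, followed by an illustration.

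**1. Definitions.** Section 9.1.1 (adverse event) and section 9.1.4 (device adverse event) both count an event whether or not it has a causal link to the product or device. Section 9.1.4 also takes in events from the procedures of using the device. Section 9.1.5 brings causation back as a condition of reporting, for listed events only. The two rules give different answers for the same event.

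**2. The presumption of unrelatedness.**
- Section 2.1: "prolonged toileting can lead to complications such as haemorrhoids, anal fissures, dilation of the sigmoid colon, autonomic dysreflexia and pressure injuries". Three of these (haemorrhoids, dysreflexia, pressure injury) are on the EO list. If TAI shortens toileting as hoped, their frequency should depend on arm.
- Section 6.2.1 has as a qualifying item "experienced autonomic dysreflexia in response to bowel care", and another covers rectal symptoms including bleeding haemorrhoids. The trial therefore recruits people prone to these events during bowel care.
- Section 3.2 makes reducing constipation and faecal incontinence secondary objectives. The protocol cannot expect TAI to change them and also presume them unrelated to it.

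**3. What the test does in each arm.** Under sections 4.2 and 5.1.1, controls carry on with their existing routine. An event during an unchanged routine can hardly be called a result of trial participation, so control reports will tend to zero. TAI reports depend on judgement.

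**4. Illustration.** Inputs: 12 per arm (Synopsis); event rates and attribution probabilities are assumptions. Expected number reported = 12 × event rate × probability of attribution.

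| Assumed rate, TAI v control | All events counted | TAI 50%, control 0% attributed | TAI 10%, control 0% | None attributed |
|---|---|---|---|---|
| 40% v 20% | 4.8 v 2.4 | 2.4 v 0 | 0.48 v 0 | 0 v 0 |
| 50% v 25% | 6.0 v 3.0 | 3.0 v 0 | 0.6 v 0 | 0 v 0 |

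In the first row the true difference is 4.8 − 2.4 = 2.4 participants. The reported difference runs from 0 to 2.4 depending only on attribution, and the control rate is lost throughout. If attribution were instead 50% in both arms, the counts would be 0.5 × 4.8 = 2.4 and 0.5 × 2.4 = 1.2: the ratio survives, but the difference halves to 1.2. Each unreported participant is 1/12 = 8.3% of an arm.

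**5. Route to the board.** Section 6.8 covers adverse and serious adverse events. An EO that is not attributed is, under section 9.1.5, not reported as an adverse event, and no section says that it reaches the board by another route.

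**The case against.** A reader might infer that the rule hides these harms altogether. The documents do not support that, for five reasons.

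- **Recording.** Sections 9.2 and 10.2 require EOs to be identified on the adverse event and serious adverse event forms. The section 7 schedule has adverse event checks at both baseline visits, six during weeks 1 to 6, and at both final visits, with no distinction by arm. The records may therefore exist. This stands, but neither section says that unattributed EOs are tabulated by arm or passed to the board, and section 9.1.5 can be read as meaning that they are not.
- **Constipation and incontinence.** Both are compared between arms through the Cleveland Clinic and St Mark's scores (section 4.5), whatever the attribution. This stands in part. The scores are taken only at baseline and at the end, so transient events may be missed. A participant lost to follow-up has no final score, and section 6.7.1 rules out imputation.
- **Blinding.** Participants, nurses and carers know the allocation, but section 6.5 keeps Associate Investigators blinded, and the protocol does not say which investigator judges causality. Attribution influenced by knowledge of allocation is therefore possible, not shown. The asymmetry in step 3 does not depend wholly on it, because it also follows from controls having no change of routine.
- **Scope.** Rectal bleeding as such is not on the EO list and stays under the ordinary definitions. Hypotension is listed, but nothing in the protocol links it to bowel care. Neither supports the point.
- **Direction.** Section 2.1 speaks of prolonged toileting, which TAI is meant to shorten. It does not show that TAI causes these events, and the documents do not establish that they are the harms TAI is most likely to change.

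Attributed events do reach the board, and the significant safety issue route in sections 9.2 and 10.1.6 remains open.

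**Conclusion.** The point holds as a conflict within the protocol with a practical consequence. Section 9.1.5 contradicts sections 9.1.1 and 9.1.4, rests on a presumption at odds with sections 2.1, 3.2 and 6.2.1, and sits unclearly with sections 9.2 and 10.2. Followed as written, it yields adverse-event counts for these conditions that cannot be compared between arms, and a safety board whose stated remit covers only the filtered events.

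It is strongest for autonomic dysreflexia, haemorrhoids and pressure injury, for which section 4.5 has no dedicated outcome, and weaker for constipation and faecal incontinence. The numerical effect is unknown: the figures above rest wholly on assumed rates and attribution probabilities. The primary outcome, its analysis and the sample size are untouched. This should be fixed, but it does not threaten the main result.

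**What to change.** Reconcile section 9.1.5 with sections 9.1.1, 9.1.4, 9.2 and 10.2, so that it is clear whether an unattributed EO is recorded and how it is reported. The EO label can stay. For autonomic dysreflexia, haemorrhoids, pressure injury, constipation and faecal incontinence, state that:

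1. every new or worsened occurrence is recorded in both arms at the adverse event checks already in the section 7 schedule;
2. all occurrences are tabulated by arm regardless of attribution, with the causality judgement kept as a separate item;
3. these tabulations form part of what the safety board reviews under section 6.8.

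This changes recording and reporting only. It needs about a paragraph of text, and no new visits or forms, since the checks are scheduled and the forms already flag EOs. The downside is a few more entries per participant, many of them background events in this population.

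The change is best made before data collection, because occurrences that were never written down may not be recoverable afterwards.

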9.2 Assessment and Documentation of Adverse Events

All AEs will be evaluated by seriousness, causality and expectedness (38). All EOs will be identified on the Adverse Event/Reaction case report form (CRF) to differentiate between known, unexpected AE/ARs and ADE/DAEs. The Principal Coordinator along with Site Coordinators will conduct safety monitoring and reporting requirements for this study in accordance with the attached NSW Health policy directive i.e. only report SSI's to the HREC. Adverse event reporting will be included on the annual report to the NSLHD HREC.

10 SERIOUS ADVERSE EVENT REPORTING

10.1 Definitions

10.1.1 Serious Adverse Event (SAE) / Serious Adverse Reaction (SAR)

A Serious Adverse Event (SAE) is any unforeseen medical event that occurs during clinical research that:

- results in participant death
- is life-threatening to the participant
- requires the inpatient hospitalisation or prolongation of existing hospitalisation for the participant leads to the participant having a persistent or significant disability/incapacity.
- leads to a congenital anomaly or birth defects.

In the context of a SAE/SAR definition, the term life-threatening refers to an event in which the participant was at risk of death at the time of the event, not an event that hypothetically might have caused death if it were more severe. Medical and scientific judgement should be exercised in deciding whether an adverse event/reaction should be classified as serious. Important medical events that are not immediately life-threatening or do not result in death or hospitalisation but may jeopardise the participant or may require intervention to prevent one of the other outcomes listed in the definition above will also be considered serious (37).

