10.1.3 Serious Adverse Device Effect (SADE)

A Serious Adverse Device Effect (SADE) that has resulted in any of the consequences characteristic of a serious adverse event such as:

- results in participant death
- is life-threatening to the participant
- requires the inpatient hospitalisation or prolongation of existing hospitalisation for the participant leads to the participant having a persistent or significant disability/incapacity
- leads to a congenital anomaly or birth defects (37).

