10.1.5 Anticipated Serious Adverse Device Effect (ASADE)

An Anticipated Serious Adverse Device Effect (ASADE) is an effect which by its nature, incidence, severity or outcome has been identified in the risk analysis report (37).

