10.2 Eliciting Serious Adverse Event Information

All participants and trial nursing staff will be provided with written definitions for SAE/SADE, SUSAR, USADE and SSI with trial office phone number for making contact in the event that this occurs during the trial. The details will be outlined on the Assessment and Documentation of Serious Adverse Events Form.

All SAEs will be evaluated by seriousness, causality and expectedness (38). All EOs will be identified on the Serious Adverse Event/Reaction case report form (CRF) to differentiate between known, unexpected SAE/SARs, SUSARS, and ASADE/USADEs. Additionally, the Investigators will conduct safety monitoring and reporting requirements for this study in accordance with the NSW Health policy directive PD2017_039 inclusive of any SSIs (38).

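### Section 10.1.1 makes being unforeseen part of the SAE definition, which contradicts the protocol's separate assessment of expectedness and leaves a gap for foreseeable serious events that are not device-related

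*Protocol*

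**What the plan says.** Section 10.1.1 opens its definition with "A Serious Adverse Event (SAE) is any unforeseen medical event that occurs during clinical research that" and then lists the usual consequences: death, threat to life, hospitalisation, disability, congenital anomaly. A later sentence adds important medical events that may jeopardise the participant. That sentence widens what is serious but does not lift the *unforeseen* condition.

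Other sections use different terms:

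- Section 9.1.1: an adverse event "is any untoward medical occurrence in a participant administered a pharmaceutical product". Section 9.1.4 (device adverse event) also uses *untoward*, whether or not the event is device-related.
- Section 9.1.3: an adverse device effect "is any adverse event related to the use of an investigational medical device".
- Section 10.1.2: a SUSAR must be both unexpected and serious, as two conditions.
- Section 10.1.3: a serious adverse device effect is one "that has resulted in any of the consequences characteristic of a serious adverse event such as" the listed outcomes, with no requirement that it be unforeseen.
- Section 10.1.5: an anticipated serious adverse device effect "is an effect which by its nature, incidence, severity or outcome has been identified in the risk analysis report".
- Section 10.2: "All SAEs will be evaluated by seriousness, causality and expectedness (38"), and "All EOs will be identified on the Serious Adverse Event/Reaction case report form (CRF") so that known and unexpected events can be told apart.
- Section 9.1.5: a listed Expected Occurrence is reported as an adverse event only if the investigator considers it a result of taking part in the trial.
- Section 6.8: "All Adverse and Serious Adverse Events will be reviewed by a safety monitoring board".

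**The concern.** Seriousness describes the consequence of an event. Expectedness describes whether it was known in advance. If an event must be unforeseen to be an SAE, a foreseeable death or hospitalisation is not one, and grading SAEs for expectedness has nothing left to separate.

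The wording reaches the people who report first. Under section 10.2, participants and trial nurses receive written definitions of SAE/SADE, SUSAR, USADE and SSI, with a number to phone. The category that expressly names anticipated events (ASADE) is not on that list. SADE is on it, but to use it the reporter must first attribute the event to the device.

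At stake are the completeness of the serious-event record and its comparability between arms. Section 6.8 makes safety concern the ground for stopping the trial.

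**Working it through.** The protocol gives no figure on this point and no calculation applies. The check follows four kinds of foreseeable serious event through the definitions, taking each section at its word.

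**1. Device-related, irrigation arm.** Not an SAE under 10.1.1, because it was foreseen. It is an adverse device effect (9.1.3), a serious one by consequence (10.1.3) and an anticipated one if it is in the risk analysis report (10.1.5). Section 10.2 names anticipated device effects among the classes to be separated on the serious-event form. It is captured and goes to the board.

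**2. Not device-related, not on the Expected Occurrence list.** Not an SAE under 10.1.1, and it has no device route. Control participants continue with enemas, suppositories or digital methods (5.1.1, 5.1.2, and the synopsis on standard bowel care), so a foreseeable serious event from their bowel care is of this kind. It is still untoward, so it is an adverse event under 9.1.1 or 9.1.4. Section 9.2 evaluates all adverse events for seriousness, and 6.8 sends it to the board. It is therefore graded serious but is not an SAE by definition.

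**3. Listed Expected Occurrence, serious, attributed to the trial.** Reported as an adverse event under 9.1.5 and seen by the board. It is an SAE only if 10.1.1 is not taken literally. If attributed to the device, it is also a SADE.

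**4. Listed Expected Occurrence, serious, not attributed to the trial.** An example is hospitalisation for urinary tract infection, pressure injury or autonomic dysreflexia. A condition listed in advance is hard to call unforeseen, so 10.1.1 excludes it. Section 9.1.5 keeps it from being reported as an adverse event. Section 10.2 says Expected Occurrences are identified on the serious-event form, but that presumes a form was raised, and neither definition then calls for one. It may reach neither the SAE record nor the board.

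| Foreseeable serious event | SAE as worded | Other route | Board |
|---|---|---|---|
| 1. Device-related | no | SADE/ASADE | yes |
| 2. Not device-related, not listed | no | AE/DAE | yes, as AE |
| 3. Listed, attributed | no | AE, possibly SADE | yes |
| 4. Listed, not attributed | no | none certain | uncertain |

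Case 4 is realistic in this population: autonomic dysreflexia in response to bowel care is one of the qualifying symptoms in section 6.2.1 and is also on the Expected Occurrence list.

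Comparing the arms, the device route in case 1 serves participants using irrigation. Foreseeable serious events tied to control-arm bowel care go to case 2 or case 4. The same kind of event can therefore be classed differently by arm.

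**The case against.** The strongest reply is that the other sections repair the word. SADE carries no *unforeseen* condition and is on the sheet given to participants and nurses. The board sees all adverse events, not only SAEs. Section 9.2 evaluates every adverse event for seriousness. The visit schedule in section 7 has adverse event checks at both baseline visits, through weeks 1 to 6 and at both final visits, so detection does not depend on phone calls alone. The author may also have meant *unforeseen* loosely, as untoward, in which case staff following section 10.2 would lose nothing.

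Much of this stands, and it rules out several stronger readings that a reader might infer:

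- *Recognised harms of irrigation escape serious-event capture.* Sections 10.1.3, 10.1.5 and 10.2 cover them.
- *Foreseeable serious events escape board review in general.* Section 6.8 covers all adverse events; only case 4 is in doubt.
- *A published comparison would look more favourable to irrigation.* The direction is not determined. It depends on whether device effects are tabulated with SAEs or apart from them, which the protocol does not say.
- *One misclassified event changes the safety conclusion.* With 12 per arm, one event is 1/12 = 8.3% (exact 95% CI 0.2% to 38.5%). With none, the upper limit is 1 − 0.025^(1/12) = 26.5%. The intervals overlap widely, and the comparison assumes the loss it is meant to show.

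The reply does not remove the contradiction itself, the missing SAE label in case 2, or the gap in case 4. Adverse event checks may find a case 4 event, but section 9.1.5 still says it is not to be reported unless attributed.

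**Conclusion.** The point holds as an internal contradiction with a limited practical gap. Section 10.1.1 conflicts with sections 9.1.1, 9.1.4, 10.1.2, 10.1.5 and 10.2. Followed literally, it leaves foreseeable serious events that are not device-related outside the SAE definition. For a serious Expected Occurrence not attributed to the trial, section 9.1.5 adds to the problem and board review becomes uncertain. SAE capture may differ between arms.

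The size cannot be expressed as a number of events, because the protocol gives no expected rate of serious events. The conclusion assumes that *unforeseen* is read in its ordinary sense and that a condition listed in advance counts as foreseen. If staff follow section 10.2 instead, fewer events or none would be lost, but the SAE count would then depend on which section each person applies. The correction should be made.

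**What to change.** - In section 10.1.1, replace the opening of the definition with: *an untoward medical occurrence affecting a participant during the trial, whether or not it was foreseen and whether or not it is related to the intervention, that …*, followed by the existing list of consequences.
- Keep expectedness as the separate assessment already required by section 10.2.
- Use the same wording in the definitions given to participants and nurses.
- Reconcile section 9.1.5 with section 10.2, so that an Expected Occurrence meeting a seriousness criterion is recorded as an SAE whether or not the investigator attributes it to the trial.

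The cost is one or two sentences in the protocol, the same change in the definitions sheet, an amendment submitted to the ethics committee under section 13.3, and possibly a few more SAE forms in a 24-participant trial. The sample size, visits and analysis do not change.
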